7.7.1. Study Drug Exposure

The exposure of study drug will be summarized for Category I and II subjects who received retreatment in this open-label study using OLR Population.

The number of injections of study drug given on Day 1, 22, and 43 during the retreatment phase, will be summarized using frequency counts and percentages by treatment sessions at treatment area (ie, left/right buttock) as:

- Number of subjects had treatment sessions
- Subjects received 12 injections per buttock
- Subjects received less than 12 injections per buttock
- Reason subject received less than 12 injections per buttock

The following will be summarized by treatment sessions at treatment area (ie, left/right buttock) using descriptive statistics:

- Number of injections given
- Number of dimples treated
- Average number of injections per dimple

A subject listing of overall exposure, and injection status will be provided along with the reasons for receiving less than 12 injections per treatment area and receiving less than 3 treatment sessions.

7.7.2. Adverse Events

AE will be summarized by SOC and PT. A subject will only be counted once per SOC and PT.

For AEs by severity grade (mild, moderate, severe), if a subject has multiple events occurring in the same SOC or same PT, then the event with the maximum intensity (ie, severe) will be counted.

For AEs by relationship to study drug, if a subject has multiple events occurring in the same SOC or same PT, the event with the highest association (ie, related) to study drug will be summarized.

AE will be presented in decreasing order of the incidences at SOC level and within each SOC, in decreasing order of the incidences at the PT level.

All AE summary tables will include number of occurrences of the adverse events and the count of subjects experienced the AEs.

AEs during 180-Day Observation Session: The AEs recorded from day of screening (within 14 days after or on Day 71/EOS of double-blind study) until start of Open-label Period and any

ongoing AEs from EN3835-302/303 studies at the time of screening of this study will be summarized by treatment arm (ie, CCH 1.68 mg, Placebo, and Overall) from double-blind studies (EN3835-302/303) using the Day-180 Observational Population and Prior to Day 180 Population.

An overall summary of AE will be presented and will include:

- Any AE
- Any ongoing AEs from EN3835 302/303
- Any AE of special interest
- Any serious AE
- Any mild, moderate and severe AE
- Any EN3835 302/303 study drug related AE
- Any AEs leading to study discontinuation
- Any AEs resulting in death

The following summary tables will be presented by SOC and PT:

- All AEs
- Ongoing AEs from EN3835 302/303
- All 302/303 study drug related AEs
- AEs by Severity
- Serious AEs
- AEs leading to study discontinuation
- AEs resulting in death
- AEs of Special Interest

Serious and most common non-serious AE by order of frequency (Most frequent, 2nd most frequent and 3rd most frequent) will be summarized by PT. Most common non-serious AEs are any preferred term that at least 5% of the subjects reported at least once.

Subject listings of all AEs, serious AEs, AEs leading to study discontinuation, AEs resulting in death and AEs of Special Interest will be provided for subjects in 180 Day Observational Population.

Subject listings of all AEs in 180 Day Observational Period for all screen failure subjects and Prior to Day 180 Population will also be provided.

AEs Before Retreatment: The new AEs recorded on or after Open-label Period starts but before retreatment in the open-label study will be summarized for subjects in Open-label Observation Population. This will include AEs of all Category I and II subjects recorded before retreatment and AEs of all Category III subjects.

An overall summary of new AE will be presented by subject category (ie, Category I, II, III, and Overall) and by time period as described in section 4.5.1.2, and will include:

- Any new AE
- Any new AE of special interest
- Any new serious AE

- Any new mild, moderate, and severe AE
- Any new AEs leading to study discontinuation
- Any new AEs resulting in death

The following summary tables will be presented by SOC and PT by subject category (ie, Category I, II, III, and Overall):

- All AEs
- AEs by Severity
- Serious AEs
- AEs leading to study discontinuation
- AEs resulting in death
- AEs of Special Interest

Serious and most common non-serious AE by order of frequency (Most frequent, 2nd most frequent and 3rd most frequent) will be summarized by PT. Most common non-serious AEs are any preferred term that at least 5% of the subjects reported at least once.

Subject listings of all AEs, serious AEs, AEs leading to study discontinuation, AEs resulting in death and AEs of Special Interest will be provided.

AEs During and after Retreatment: The new AEs recorded on or after retreatment in the open label study will be summarized for subjects in OLR Population. This will include AEs of all Category I and II subjects recorded after retreatment.

An overall summary of new AE and new AE related to study drug recorded after retreatment will be presented for each subject category (ie, Category I, II and Overall) by treatment sessions and time period (ie, all study periods and each study period as described in section 4.5.1.2), and will include:

- Any new AE
- Any new AE of special interest
- Any new serious AE
- Any new mild, moderate, and severe AE
- Any new AEs leading to study drug withdrawn/interruption
- Any new AEs leading to study discontinuation
- Any new AEs resulting in death

The following summary tables will be presented by SOC and PT by subject category (ie, Category I, II, and overall) and each treatment sessions [TX1, TX2, TX3, and Total ('Total' includes AEs reported during Treatment Session 1, 2, and 3, and Observation Period post Day 71 of retreatment)]:

- All AEs
- AEs by causal relationship to study drug
- AEs by Severity
- Study drug related AEs by severity
- Serious AEs

- Serious study drug related AEs
- AEs leading to study drug withdrawn/interruption
- Study drug related AEs leading to study drug withdrawn/interruption
- AEs leading to study discontinuation
- Study drug related AEs leading to study discontinuation
- AEs resulting in death
- Study drug related AEs resulting in death
- AEs of Special Interest

Serious and most common non-serious AE by order of frequency (Most frequent, 2nd most frequent and 3rd most frequent) will be summarized by PT. Most common non-serious AEs are any preferred term that at least 5% of the subjects reported at least once.

Subject listings of all AEs, serious AEs, AEs leading to study drug withdrawn/interruption, AEs leading to study discontinuation, AEs resulting in death and AEs of Special Interest will be provided.

Refer to [Table 17](#) for computation of duration of AE.

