2. STUDY OBJECTIVES

2.1. Primary Objective

The primary objectives of this study are to assess:

- The long-term safety of CCH in the treatment of EFP commonly known as cellulite in adult women
- The safety of CCH when used for retreatment in the treatment of EFP commonly known as cellulite in adult women
- The long-term immunogenicity profile of CCH following treatment of EFP commonly known as cellulite in adult women

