 - ^c Local adverse events associated with the injection site from the 302/303 studies, including acute (eg, erythema, bruising, pain, nodules/mass, ulceration, blistering, pruritus, swelling, and/or induration) and/or chronic (eg, skin thickening, fibrosclerosis, peau d’orange changes) cutaneous adverse events, will be recorded and evaluated for seriousness and severity.
- d=Days; EOS=End of study; M=Month; OBS=Observation.

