4.5.1.2. Adverse Events during Open-label Period

Adverse Event Categorization Before Retreatment

The AEs will be associated with time periods in the open label study period based on the start date of the AE compared to time period start date, as below:

- Start of Open-label Period – <Day 360 (M12)
- ≥Day 360 (M12) – <Day 540 (M18)
- ≥Day 540 (M18) – <Day 720 (M24)
- ≥Day 720 (M24) – <Day 1080 (M36)

Adverse Event Categorization after Retreatment

An AE will be associated with a treatment session during the retreatment session based on the start date of the AE compared to the date of the injections.

- AEs (which occur or worsen) with a start date between the Day 1 visit date and the day prior to the next dose or, if no further dose, the Day 71 visit date, will be associated with Treatment Session 1.
- If study drug is administered at the Day 22 visit, AEs (which occur or worsen) with a start date between the Day 22 visit date and the day prior to the next dose or, if no further dose, the Day 71 visit date, will be associated with Treatment Session 2.
- If study drug is administered at the Day 43 visit, AEs (which occur or worsen) with a start date between the Day 43 visit date and the Day 71 visit date will be associated with Treatment Session 3.
- AEs with a start date on or after Day 71 of retreatment will be aligned with observational assessment visits as, AE occurring in time period:
 - ≥Day 71 of retreatment – <Day 360 (M12)
 - ≥Day 360 (M12) – <Day 540 (M18)
 - ≥Day 540 (M18) – <Day 720 (M24)
 - ≥Day 720 (M24) – <Day 1080 (M36)

Refer to section [6.3.1.1](#) to identify AE time period status when the start date of an AE is unknown.

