4.5.1.4. Relationship to Study Drug

Causal relationship of AE with study drug will be classified by the Investigator and will be reported as follows:

- Not related

- Unlikely related
- Possibly related
- Probably related

Related adverse events are AEs with the relationship described by the investigators as “probably related” or “possibly related”. “Not related” or “Unlikely related” causality assessments are considered as negative causality.

The ongoing AE’s from EN3835 302/303 studies at the time screening will be imported in the open label study and their relationship with study drug in EN3835 302/303 will also be classified as above.

Any missing relationship of an AE to study drug will be considered as related to study drug for the analyses, following worst case principle.

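### In the open-label period before retreatment, the planned AE tables show no AEs related to the 302/303 study drug and no AEs persisting from earlier; both appear only in subject listings

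*SAP*

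**What the plan says.** The first primary objective in SAP 2.1 is "The long-term safety of CCH in the treatment of EFP commonly known as cellulite in adult women". Section 7.7.2 plans the AE outputs in three blocks.

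- **Screening to the start of the Open-label Period.** The overall summary includes AEs ongoing from the double-blind studies and "Any EN3835 302/303 study drug related AE". Each also has a SOC/PT table.
- **Open-label Period before retreatment.** The block opens with "The new AEs recorded on or after Open-label Period starts but before retreatment in the open-label study will be summarized" and defines its coverage: "This will include AEs of all Category I and II subjects recorded before retreatment and AEs of all Category III subjects". The overall summary and the SOC/PT tables deal with all AEs, special interest, severity, seriousness, discontinuation and death. Neither list has a relationship item or an ongoing item. Subject listings of all AEs are planned.
- **During and after retreatment.** This block is also confined to new AEs, but it has a full set of study-drug-related summaries.

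Section 4.5.1.2 places pre-retreatment open-label AEs in time periods "based on the start date of the AE compared to time period start date". Section 4.5.1.4 has the investigator classify causality without limiting this to any period, and adds: "Any missing relationship of an AE to study drug will be considered as related to study drug for the analyses". Table 4, footnote c, has Category III subjects assessed at Months 12, 18, 24 and 36 for "Local adverse events associated with the injection site from the 302/303 studies", with chronic skin changes among the examples. Section 7.7.2 closes by pointing to Table 17 "for computation of duration of AE", but specifies no summary of duration.

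**The concern.** The study follows subjects for up to three years after Day 71 of the double-blind study, and chronic local changes at the injection site are a named target of that follow-up. Two questions follow for a long-term safety objective: how many later AEs were judged related to the earlier treatment, and how many earlier injection-site changes are still present. In the pre-retreatment open-label block no specified table answers either.

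This matters most for Category III. These subjects cannot be retreated, and Table 4 schedules no laboratory or vital-sign assessments for them from Day 360 on. Sections 7.7.1 to 7.7.7 specify no separate summary of the local safety assessments. The AE tables are therefore the only specified summary route for what those visits find locally.

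**Working it through.** **Step 1. Compare the three blocks of 7.7.2.**

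| Item | Screening to open-label start | Open-label, before retreatment | During and after retreatment |
|---|---|---|---|
| Events counted | AEs from screening on, plus those ongoing from 302/303 | New AEs only | New AEs only |
| Related AEs, overall summary | Yes (302/303 drug) | No | Yes |
| Related AEs, SOC/PT | Yes (302/303 drug) | No | Yes |
| Related AEs by severity | No | No | Yes |
| Ongoing AEs | Yes, imported from 302/303 | No | No |
| Duration summary | No | No | No |
| Subject listing of all AEs | Yes | Yes | Yes |

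The middle block is the only one with no relationship output. The absence of dosing in that interval does not explain this: no drug is given in the first block either, and that block attributes AEs to the 302/303 drug. Section 4.5.1.4 supplies the causality data and the missing-value rule, and the opening of 7.7.2 supplies a counting rule by relationship. No table in the middle block uses them.

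**Step 2. Follow one event.** Take a skin thickening that began in 302/303, does not worsen, and is still present at Day 1080 in a Category III subject. It is imported at screening and counted in the 180-day tables. Its start date precedes all four pre-retreatment open-label periods in 4.5.1.2, so it enters none of them. In the summary tables it cannot be told apart from one that resolved soon after screening. If it worsens, 3.11.1 gives it a new onset date and it enters as new.

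**Step 3. Length of the interval.** The inputs are end of follow-up at Day 1080 (SAP 3.1.3) and an assumed Open-label Period start at Day 180.

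- Category III and never-retreated Category I/II: (1080 − 180) / 1080 = 900 / 1080 = 83.3%.
- Retreated at day r: (r − 180) / 1080. This gives 0% at Day 180, 180/1080 = 16.7% at Day 360, 360/1080 = 33.3% at Day 540, and 540/1080 = 50% at Day 720.

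The SAP does not state the retreated share. As an assumption, let a fraction f of all subjects be retreated at day r between 180 and 540, with everyone followed to Day 1080. The affected share of planned follow-up is [(1 − f) × 900 + f × (r − 180)] / 1080.

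| f | r = 180 | r = 540 |
|---|---|---|
| 0 | 900/1080 = 83% | 83% |
| 0.25 | 675/1080 = 63% | 765/1080 = 71% |
| 0.50 | 450/1080 = 42% | 630/1080 = 58% |
| 0.75 | 225/1080 = 21% | 495/1080 = 46% |

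**The case against.** The strongest reply is that no event is lost. AEs ongoing from 302/303 or starting before the Open-label Period are tabulated once in the 180-day block, including by severity and by relationship to the 302/303 drug. Worsening re-enters as new. Late-onset local changes appear in the pre-retreatment tables of all AEs and by severity. All AEs are listed by subject, and 6.1 promises listings of all CRF data and derived variables, so causality and duration can be read there. Counting by new onset is the SAP's consistent rule for the open-label phase. The 180-day ongoing row is a one-time import from other studies, not a carry-forward between periods. The table shells in SAP Module 2 are not shown.

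Most of this stands, and it limits the point. A reader might infer that a persistent reaction would look like a clean record. The documents do not support that, because the event is counted at onset and listed. A reader might also infer that the study reports no related AEs after Day 180. That is wrong too: for retreated subjects, related AEs are tabulated through the treatment sessions and the observation after them.

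The reply does not remove the gap. A listing gives no count or percentage by category. The missing relationship output departs from both neighbouring blocks, and no reason is given. The 180-day relationship table cannot cover AEs that start later.

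**Conclusion.** The point holds for the summary tables. From the start of the Open-label Period until retreatment, or until end of study if never retreated, 7.7.2 specifies no table of AEs related to the 302/303 drug and none showing unchanged AEs that persist from earlier. The relationship omission is the firmer half, since the SAP is inconsistent across its own blocks. The persistence gap follows from a rule applied consistently, but that rule fits a long-term safety objective poorly when chronic local effects are being monitored.

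The 83% applies only to Category III and never-retreated Category I/II subjects, and only if the Open-label Period starts at Day 180. Table 1, footnotes e and l, allow unblinding and category assignment to come later, which would shorten the interval. It is tempting to say the gap covers most of the whole study's follow-up. The SAP does not support this, because the share and timing of retreatment are not stated; under the assumptions shown, the figure runs from 21% to 83%. The change should be made, but it affects reporting rather than design or data collection.

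**What to change.** In the pre-retreatment block of SAP 7.7.2, add:

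- **Related AEs.** Include AEs related to the 302/303 study drug in the overall summary, by category and by the periods of 4.5.1.2, and in a SOC/PT table, as the 180-day block does. Apply the 4.5.1.4 rule for missing causality.
- **Persisting AEs.** Add a row and a SOC/PT table of AEs ongoing at the start of the Open-label Period, by category, with the number of local or injection-site AEs still unresolved at last contact. This is a new output; the 180-day import row is not an exact model for it.

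Related AEs by severity and a summary of AE duration are optional. Only the retreatment block has the first, and no block has the second.

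The cost is a few extra tables and their shells, from data already collected. Eligibility, visits and the other AE blocks are unaffected.

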5. ANALYSIS POPULATIONS

The study will use following analyses population for data summarization.

Table 16: Analysis Population

Population	Definition	Displays
Day-180 Observational Population	The Day-180 Observational Population includes all rollover subjects from studies EN3835-302/303.	The protocol deviations, demographic characteristics and safety analysis for the data obtained from Screening to Day 180 will be based on this population. The reduction of response, complete loss of response, and all cellulite assessments (ie, changes in CR-/PR-PCSS, PR-CIS, S-GAIS, SSRS, and subject satisfaction with cellulite treatment at Day 180 will be summarized.
Prior to Day 180 Population	Prior to Day 180 Population includes all subjects who did not meet inclusion criteria #2 or inclusion criteria #5 or those who withdrew from the study due to SAE/AE, or lost to follow-up prior to Day 180.	The protocol deviations, demographic characteristics and safety analysis for the data obtained from Screening to Day 180 will be based on this population.
Open Label Observation Population	The Open Label Observation Population includes all subjects who enter the open-label study and received active CCH in EN3835-302 or EN3835-303. This population will include all Category I, II, and III subjects including the subjects who received retreatment in the Open-label Period.	The protocol deviations, demographic characteristics and safety parameters for the open label period prior to retreatment will be summarized based on this population.
Time to Reduction of Response (TRR) Population Before Retreatment	The TRR Population Before Retreatment includes all subjects who have at least a 1-level or 2-level improvement in both CR-PCSS and PR-PCSS ratings during the double-blind study for either/both treated buttocks. This population will include Category I and II subjects. Reduction of response will be evaluated separately for subjects who have at least a 1-level and 2-level improvement in both CR-PCSS and PR-PCSS ratings during the double-blind study in each treated buttock. The reduction of response prior to retreatment will be analyzed using this population.	The analyses of cellulite assessments prior to retreatment, and demographic characteristics will be based on this population.

Table 16: Analysis Population (Continued)

Population	Definition	Displays

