6. STATISTICAL METHODS

6.1. General Methodology

All summary tables and data listings will be prepared using version 9.4 or later of statistical analysis software (SAS®) software.

Continuous data will be summarized using descriptive statistics (number of subjects [n], mean, standard deviation [SD]/ or standard error [SE], median, minimum [min], and maximum [max]) and discrete data will be summarized using frequency counts and percentages, the denominator will be based on the number of subjects in the appropriate population. For the purpose of display, the summary results will be rounded as follows:

- Min and max: same number of decimal places as the raw data.
- Mean and median: one more decimal place than the raw data.
- SD/SE: two more decimal places than the raw data.
- Percentages will be displayed with one decimal precision. A zero count will not have the associated percentage presented on the table (ie, no 0%).
- The standard form of a percentage change variable is 0 decimal places.

For categorical variables with missing values, a category documenting the frequency of missing values will be displayed in the summary tables.

Summary tables, subject listings, graphs and any supportive SAS output will include a “footer” of explanatory notes that will indicate, when applicable:

- Date of data extraction
- Date and time of output generation
- SAS program name, including the path, that generates the output

When calculating percentages, the denominator will be based on the number of subjects with non-missing values. If the denominator is expected to change over time, then the denominator used to calculate the percentage should be based on the number of subjects with non-missing values at each visit. Any subject removed from an analysis will be noted at the bottom of the table along with the reason the subject was removed.

Null summary tables will be presented with a note stating that “No Subjects Met Criteria.” Subject listings of all data from the CRFs as well as any derived variables will be presented.

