7.6.2. Reduction of response using PR-PCSS and CR-PCSS Prior to Retreatment

The proportion of subjects or buttocks with reduction of response (refer to section 4.4.1) will be summarized using frequency counts and percentages using TRR Population Before Retreatment and OLNLR Population subject category (ie, Category I and II, and Overall) and treatment area (ie, left and/or buttock) at the following visits prior to retreatment: Day 180, Month 12, 18, 24, and 36 where reduction of response is assessed.

The proportions will be computed based upon number of subjects within each category and treatment area remains not-retreated prior to that visit.

The following efficacy end points for reduction of response will be summarized:

- Proportion of subjects with 2-level composite reduction
- Proportion of subjects with 1-level composite reduction
- Proportion of subjects with complete loss of response

The time to composite reduction of response (ie, by 1-level and 2-level separately) and time to complete loss of response (refer to section 4.4.1 for derivation) will be summarized descriptively using TRR Population Before Retreatment and OLNLR Population.

The listings of cellulite PR-PCSS and CR-PCSS severity ratings will be provided for All Subjects prior to retreatment.

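### Pre-retreatment AE percentages by period have no at-risk denominator: under the Section 6.1 default, retreated and departed subjects stay in the divisor and late-period incidence is understated

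*SAP*

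**What the plan says.** **Numerator.** Under AEs Before Retreatment, Section 7.7.2 defines the events counted: "This will include AEs of all Category I and II subjects recorded before retreatment and AEs of all Category III subjects". The overall summary is given by category "and by time period as described in section 4.5.1.2". Section 4.5.1.2 sets the rule: "The AEs will be associated with time periods in the open label study period based on the start date of the AE". The periods are open-label start to Day 360, Day 360 to 540, Day 540 to 720 and Day 720 to 1080. The SOC/PT tables before retreatment are by category only.

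**Population.** The events "before retreatment in the open-label study will be summarized for subjects in Open-label Observation Population". Table 16 in Section 5 defines that population: "This population will include all Category I, II, and III subjects including the subjects who received retreatment in the Open-label Period". Nothing there removes a subject at retreatment or discontinuation.

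**Denominator.** Section 7.7.2 names none. Section 6.1 sets the general rule for discrete data: "the denominator will be based on the number of subjects in the appropriate population". A further sentence there begins: "If the denominator is expected to change over time, then the denominator used to calculate the percentage should be based on". What follows ties the divisor to those whose value is recorded at the visit concerned.

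**Efficacy, for comparison.** Section 7.6.2 deals with the same problem for reduction of response: "The proportions will be computed based upon number of subjects within each category and treatment area remains not-retreated prior to that visit".

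**The concern.** A Category I subject retreated before Month 12 cannot contribute a Month 18 to 24 event to the pre-retreatment table, because her later events belong to the retreated summaries. She nevertheless remains in the population by which, under the default, that period's count is divided. A subject who has left the study is in the same position. The percentage therefore falls from period to period as the risk set shrinks, even if the AE rate among those still under observation is constant.

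Long-term safety heads the primary objectives in Section 2.1. A reader of the by-period table would naturally ask whether AEs become less frequent with time and whether the three categories differ. Both comparisons would be affected. Reduction of response, which is only a secondary objective, has a not-yet-retreated denominator; the pre-retreatment AE summary does not.

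**Working it through.** The SAP states no AE rate, retreatment share or dropout share, so there is no figure of its own to reproduce. The check is of direction, with assumed inputs.

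**1. Formula.** Let *f* be the fraction of a category still in the study and not yet retreated at the start of a period. If nobody leaves the risk set within the period,

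shown % = at-risk % × *f*, and relative understatement = 1 − *f*.

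**2. Range of *f* (assumed), true period incidence 10% (assumed).**

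| *f* | Shown, whole population | Shown, at-risk denominator |
|---|---|---|
| 0.9 | 10 × 0.9 = 9% | 10% |
| 0.7 | 10 × 0.7 = 7% | 10% |
| 0.5 | 10 × 0.5 = 5% | 10% |
| 0.3 | 10 × 0.3 = 3% | 10% |

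**3. By category.** Take *f* = (1 − retreated share) × (1 − dropout share), assuming the two are independent. All shares are assumed, except that Category III retreatment is zero under Section 3.1.3.

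| Category | Retreated | Dropout | *f* | A true 10% shows as |
|---|---|---|---|---|
| I | 60% | 20% | 0.4 × 0.8 = 0.32 | 3.2% |
| I or II | 30% | 20% | 0.7 × 0.8 = 0.56 | 5.6% |
| II | 10% | 20% | 0.9 × 0.8 = 0.72 | 7.2% |
| III | 0% | 20% | 1 × 0.8 = 0.80 | 8.0% |
| III | 0% | 40% | 1 × 0.6 = 0.60 | 6.0% |

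At equal dropout, identical true incidence appears as different percentages purely because of retreatment. With 40% dropout, Category III (6.0%) falls below a Category II with 10% retreated and 20% dropout (7.2%). The ordering is therefore not fixed by design.

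**4. Period length.** From the boundaries in Section 4.5.1.2: 540 − 360 = 180 days, 720 − 540 = 180 days, 1080 − 720 = 360 days. The first period starts at open-label entry. The footnotes to Table 1 allow unblinding and category assignment at Day 180 or at a later unscheduled visit, so this period's length is subject-specific. At a constant rate that gives 10% over 180 days, 360 days gives 1 − 0.9² = 19%. With *f* = 0.5 this would show as 9.5%. Length and dilution thus pull in opposite directions, and the crude series across periods cannot be read as a trend in rate.

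**5. Tables not split by period.** In the SOC/PT tables by category, all subjects are at risk at open-label start, so the count at entry is a legitimate divisor. Pre-retreatment follow-up still differs by category. Category I can qualify for retreatment on severity ratings (Table 2, footnote n), Category II needs a confirmed loss of response (Section 3.2.1.5), and Category III is never retreated. Crude percentages do not reflect this, and neither does the 5% cut-off for common non-serious AEs.

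**The case against.** The strongest reply is that the SAP never prints this divisor. Section 7.7.2 names the population summarised and promises occurrences and subject counts, and Section 6.1 itself foresees denominators that change over time. Section 11 places table layouts and footnotes in SAP Module 2, which is not at hand and could settle the matter. The split by period affects only the short overall summary, no test between categories or periods is planned, and Section 7.1 reports discontinuations by period and time in study. Part of the shrinking risk set is therefore visible.

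Some of this stands. A reader might infer that the SAP expressly divides period counts by the whole population; it does not, and the conclusion rests on the Section 6.1 default. The changing-denominator sentence is no clear remedy, however. It relies on non-missing values at a visit, whereas AE periods are date intervals, and a subject with no AE record has no event rather than a missing value. Percentages are evidently intended, since Section 6.1 prescribes them for discrete data and Section 7.7.2 orders AEs by incidence and applies the 5% threshold.

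A reader might also infer that the understatement falls mainly on Categories I and II. The SAP does not support that, because dropout dilutes Category III too and no uptake or dropout shares are given.

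**Conclusion.** The point holds as a defect in how the pre-retreatment AE summaries are specified. The numerator is cut at retreatment, the population is not, and the only general divisor that clearly applies is the population count. Under that default, period percentages are understated by 1 − *f*, the fraction of the category no longer at risk at period start. Retreatment contributes to this in Categories I and II only; discontinuation contributes in all three.

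The actual size is unknown. The figures of 3% to 9% for a true 10% rest on assumed fractions, and on nobody leaving the risk set during a period. Unequal time at risk is a separate problem. It affects comparisons between periods, and it also affects the SOC/PT tables by category. The change should be made because it bears on a primary safety objective and Section 7.6.2 already contains the matching principle.

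**What to change.** In Section 7.7.2, under AEs Before Retreatment:

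- Make exposure-adjusted incidence the main summary by category and by period, giving both subjects with events and events per 100 subject-years. Time at risk runs from open-label start, or period start, to the earliest of first retreatment injection, discontinuation or last date in study (or period end, for period rates).
- For the crude percentages in the by-period overall summary, show and use as denominator the number of subjects in the study and not yet retreated at the start of each period, by category, matching Section 7.6.2.
- Give subject-years alongside the SOC/PT tables by category.

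The start-of-period denominator is not enough by itself. A subject retreated soon after a period begins would still count fully in it while contributing few days, which is why the exposure-adjusted rate should lead.

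The cost is SAP wording and modest programming. Table 17 already derives the first retreatment injection date and the last date in study; it has no entry for the open-label start date, so one should be added. Late-period percentages will look less favourable than under the default.
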